### **Ineligibility Criteria**

- Distant metastases, based upon:
  - CT scan or MRI of the abdomen/pelvis or PSMA PET/CT within 120 days prior to registration and
  - Bone scan or PSMA PET/CT within 120 days prior to registration; if the bone scan is suspicious, a plain x-ray and/or MRI must be obtained to rule out metastasis prior to registration.
- Patient is unable or unwilling to sign consent.
- Patient is considered low-risk and would not have received adjuvant RT outside of this study

## **REGISTRATION PROCEDURES**

### **General guidelines**

Subjects will be identified by physicians in Urology or Radiation Oncology. The Study Coordinator will enter eligible patients on study centrally at the UCLA Jonsson Comprehensive Cancer Center. Subjects will be recruited through self-referral and the advice of their attending physician.

### **Registration process**

A member of the research team will enroll the patient onto the trial. Consent will be obtained after a clear and thorough discussion between the patient and the principal investigator or any of the co-investigators in clinic. Any patients that are deemed by the principal investigator or co-investigators to be mentally or physically incapable of consent will not be included in the study.

Once a candidate has provided full consent, the following will be completed/collected to fully determine eligibility:

- Signed patient informed consent form
- HIPAA authorization form
- Medical history, clinical examination and consultations with Radiation

Oncology and Interventional Radiology departments

- Verification of clinical stage  $\geq$  T3 (staging by imaging acceptable)
- Verification of no distant metastases, based upon:
  - CT scan or MRI of the abdomen/pelvis or PSMA PET/CT within 120 days prior to registration and
  - Bone scan or PSMA PET/CT within 120 days prior to registration; if the bone scan is suspicious, a plain x-ray and/or MRI must be obtained to rule out metastasis

REGISTRATION

Study team will register subject with the UCLA Data Safety Monitoring Board to assure eligibility, prior to undergoing any further study-related procedures.

#### PRIOR TO RADIATION TREATMENT

Prior to radiation treatment, approximately 60 mLs of blood will be drawn for serum translational biomarker study.

### **TREATMENT PLAN**

#### **Radiation Simulation:**

Enrolled patients will undergo radiation simulation and planning as per routine for prostate cancer patients. A custom vacloc bag, alpha cradle, or equivalent immobilization device. A simulation scan will be performed. A pelvic mp MRI will be obtained if not available within the prior 4 months. The MRI will be utilized as a supplement for anatomical contour delineation. The urethra will be delineated with the MRI. These procedures are considered standard-of-care for prostate radiotherapy planning.

#### **Radiation Planning (Target Areas):**

- The study investigator will delineate the prostate, seminal vesicles on the pelvic simulation CT.
- The prostate PTV will consist of an expansion of the prostate gland up to 7mm in all directions, (expansion may be reduced to 3mm posteriorly).
- The SV PTV will consist of the contoured SV without expansion.
- For all PTVs, the Prescription Dose will be defined to cover 95% of the PTVs.
- Target Prescription Doses:

Prostate	24 Gy in 3 fractions, 8 Gy per fraction
SV (if involved)	24 Gy in 3 fractions, 8 Gy per fraction
- Technique: image-guided SBRT via robotic radiosurgery, IMRT, or VMAT, with daily and intra-fraction Image-guidance fiducial-based, CBCT-based, MRI-based.

Immediately after the 3rd (final) fraction of radiation treatment up to 4 weeks post SBRT, approximately 60 mls of blood will be drawn for serum translational biomarker study.

#### **Prostatectomy:**

Radical prostatectomy will be performed, either open or robot assisted, within 4 weeks after SBRT (preferably 2 weeks). After resection, the prostate is sectioned from base to apex into 5-7 slices depending on the size of the prostate. Slices 2 and 4 are kept fresh on ice, while all other slices are fixed in formalin and embedded in paraffin. A slide is cut and stained from the paraffin sections for pathologic diagnosis and the remaining tissue will be kept indefinitely in pathology and can be used for research.

Frozen section is prepared from the fresh tissue (slices 2 and 4) for rapid diagnosis. Part

of the fresh tissue is used for research and the remaining fresh tissue is frozen indefinitely and can be used for research.

**Follow-up:**

- 0 to 4 weeks after the final fraction of radiation, patients will have approximately 60 mLs of blood drawn for serum translational biomarker research. Patients will also be evaluated by their physician and Adverse Events and Concomitant Medications will be assessed. EPIC and IPSS questionnaires will also be administered at this time.
- Patients are followed every three months ( $\pm$  4 weeks) for one year post surgery. At each follow-up visit, patients are evaluated for CTCAE (version 4.0) toxicity scores, and the EPIC and IPSS questionnaires will be administered. Blood draws (~5 mLs) to assess PSA are drawn at each of the follow-up visits unless PSA lab evaluations have already been done within 4 weeks of the study visit. In addition, at the 3 month and 6 month follow-up visits, approximately 60 mLs of blood will be drawn for serum translational biomarker study. After one year of follow-up, patients will be seen as per routine care.

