- Patients will receive 3 fractions of 8Gy delivered by SBRT over 1-2 weeks, 2-4 weeks prior to prostatectomy and will come to clinic for standard follow-up for one year after surgery.

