**Protocol Overview**

SBRT	Prostatectomy	Tests at each Follow-up
24Gy in 3 fractions (8 Gy per fraction)	Open or robotic assisted prostatectomy within 4 weeks (preferable 2 weeks) of SBRT	CTCAE toxicity scores, QOL-EPIC & IPSS scores, blood (including PSA)

[figure not shown]
Study Design: Prospective Phase I  
 Sample size: 12 patients, single-institutional  
 Outcome: Feasibility assessment (percent of patients completing scheduled treatment)  
 Treatment: SBRT, prostatectomy  
 RT targets: Prostate PTV = prostate and SV (only if involved on MRI or biopsy)

Target Prescription Doses:

Prostate PTV 24 Gy in 3 fractions, 8 Gy per fraction

RT Technique: image-guided SBRT via robotic radiosurgery, IMRT, or VMAT, with daily and intra-fraction Image-guidance (MRI-based, fiducial-based or CBCT-based)

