#### **• Secondary Objectives:**

- To assess safety and acute toxicity of SBRT followed by prostatectomy. This will be based on CTCAE version 4.0 and patient reported quality of life (EPIC and IPSS questionnaires).
- Investigation of the radiobiology of SBRT in prostate cancer using resected prostate tumor tissue. For the correlative genomic analyses, prostate lesions at the time of prostatectomy will be processed for RNA and exome sequencing and compared to existing sequencing data for localized prostate cancers. We will utilize both supervised and unsupervised analyses of

- Pathway activation from RNA-seq data sets in order to determine which pathways are enriched after irradiation.
- Evaluation of the nature of the immune response to prostate cancer generated by SBRT.
    - Systemic immune response. Blood that is collected pre SBRT, between 0 and 4 weeks after SBRT, and at 3 and 6 month intervals after SBRT will be assessed as follows: PBMCs will be isolated over Ficoll-gradients and stored frozen until analysis. Lymphoid and myeloid subset phenotyping will be assessed by antibody staining and multi-color flow cytometry (LSR-Fortessa, BD). Circulating cytokines, PGE2, prostate-tumor specific antibodies, HMGB-1 protein and the tryptophan/kynurenine ratio in plasma will be quantified by ELISA. Tumor-specific CD4 and CD8 T cell activities to known HLA-matched, immunodominant, tumor-associated antigens will be assessed ex vivo by IFN  $\gamma$  -ELISPOT and dextramer staining. The tumor antigens of choice will include PSA and PSMA.
    - Local immune response. The immune response at the tumor site will be visualized through immunohistochemistry (IHC), with particular focus on T cells (CD3+), T regulatory cells (CD4+ CD25hi), tumor infiltrating myeloid-derived suppressor cells (CD11b+ Gr-1+ CD15+) and tumor-associated macrophages (CD11b+F4/80+). Levels of CSF1/CSF1R, tumor MHC I, PD-1 and PD-L1 are also of interest as are markers for EMT (vimentin, N-cadherin, E-cadherin), for neuroendocrine differentiation (chromogranin A, neuron specific enolase), AR protein and p53. Comparisons will be made to pre-treatment biopsy material when possible and to tissue microarrays of non-irradiated prostatectomy specimens.

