**Measurements of serological markers (secondary objective).** Circulating cytokines, PGE2, prostate-tumor specific antibodies, HMGB-1 protein and the tryptophan/kynurenine ratio in plasma will be quantified by ELISA. Tumor-specific CD4 and CD8 T cell activities to known HLA-matched, immunodominant, tumor-associated antigens will be assessed ex vivo by IFN $\gamma$ -ELISPOT and dextramer staining. The tumor antigens of choice will include PSA and PSMA. A repeated measures analysis of variance will be used to assess differences in these serological markers over time. In addition to the overall time effect in the ANOVA model, we plan to test specific contrasts

between serological markers pre-treatment (baseline) and the first measurement post SBRT (pre surgery), where we anticipate to observe an increase in circulating tumor-specific CD4 and CD8 T cell activity.

Multivariate profile analyses may be used when patterns for various markers emerge. These statistical analyses will be performed using IBM SPSS Statistics for Windows, Version 20.0. (Armonk, NY) statistical software.

**Measurements of intra-tumoral and intra-prostatic markers (secondary objective).** The immune response at the tumor site will be visualized through immunohistochemistry (IHC), with particular focus on T cells (CD3+), T regulatory cells (CD4+ CD25hi), tumor infiltrating myeloid-derived suppressor cells (CD11b+ Gr-1+ CD15+) and tumor-associated macrophages (CD11b+F4/80+). Levels of CSF1/CSF1R, tumor MHC I, PD-1 and PD-L1 are also of interest as are markers for EMT (vimentin, N-cadherin, E-cadherin), for neuroendocrine differentiation (chromogranin A, neuron specific enolase), AR protein and p53. IntMax (scale of 0-300) = (% of positive tumor cells [scale of 0-100]) X (intensity of staining based on 0-3 scale [scale of 0-3]) will be assessed for each marker. Comparisons in markers will be made between: 1- post SBRT prostatectomy specimens vs biopsy material pre-SBRT; and 2- post SBRT prostatectomy specimens vs archival tissue of prostatectomy specimens (that did not undergo RT).

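### The first post-SBRT research blood draw may be taken after prostatectomy under the collection window, although the planned contrast needs a pre-surgery sample

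*Combined protocol and SAP*

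**What the plan says.** The serological-markers paragraph of STATISTICAL CONSIDERATIONS plans a repeated measures ANOVA over time and, within it, a specific contrast of baseline against "the first measurement post SBRT (pre surgery), where we anticipate to observe an increase in circulating tumor-specific CD4 and CD8 T cell activity". This is the only serological comparison with a stated expected direction. The baseline is clear: "Prior to radiation treatment, approximately 60 mLs of blood will be drawn" (PRIOR TO RADIATION TREATMENT).

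The timing of the second sample is set in four places, and OUTCOME MEASURES adds only that it follows completion of SBRT:

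- Follow-up: "0 to 4 weeks after the final fraction of radiation, patients will have approximately 60 mLs of blood drawn".
- Secondary Objectives: "between 0 and 4 weeks after SBRT, and at 3 and 6 month intervals after SBRT".
- Radiation Planning (Target Areas): a sentence that begins with the word *immediately* and continues to the four-week limit, in part "final) fraction of radiation treatment up to 4 weeks post SBRT, approximately 60 mls of blood will be drawn".
- TABLE OF STUDY ASSESSMENTS: a column for weeks 0 to 4 after SBRT, placed just before the column that holds prostatectomy.

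Surgery falls in the same period. The Protocol Overview has "Open or robotic assisted prostatectomy within 4 weeks (preferable 2 weeks) of SBRT", and the Prostatectomy section agrees: "within 4 weeks after SBRT (preferably 2 weeks". The Design bullet at the front of the protocol places SBRT "2-4 weeks prior to prostatectomy".

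**The concern.** A patient operated on at week 2 and bled at week 3 has followed every scheduling rule, yet the sample is not the one that the contrast describes. The plan does not say what to do with it. Keeping it in the contrast adds whatever surgery and removal of the tumour do to these markers to whatever SBRT does. Leaving it out removes one pair from at most 12.

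No other sample can stand in. Follow-up times the 3- and 6-month visits from surgery. Even if those draws are dated from SBRT, as in Secondary Objectives, they come after any operation done within four weeks. This draw is therefore the only one that can show a change after SBRT separately from surgery, and a pre-operative sample that was never taken cannot be recovered at analysis.

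The trial's own checks would not catch the problem. DATA and SAFETY MONITORING requires approval for procedures outside their window, but this draw would be inside it.

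**Working it through.** The plan gives no figure on this point to reproduce. The check compares two windows and then illustrates what the overlap could mean.

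**Inputs from the documents.** The draw window is days 0 to 28 after the final fraction (Follow-up, Secondary Objectives, Radiation Planning, TABLE OF STUDY ASSESSMENTS). Surgery is due by day 28, preferably at day 14 (Protocol Overview, Prostatectomy), or between days 14 and 28 (Design bullet). The sample size is 12 (STATISTICAL CONSIDERATIONS).

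**Step 1: do the windows overlap?** Yes, under either statement of surgery timing. For surgery on day S, the share of the permitted draw window that lies after surgery is (28 − S)/28:

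- S = 14: 14/28 = 50%
- S = 21: 7/28 = 25%
- S = 28: 0/28 = 0%

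**Step 2: illustration of numbers affected.** Assume that the draw day is uniform over days 0 to 28 and independent of the surgery date. The documents support neither assumption; they give no distribution.

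- All surgery on day 14: 50%, or 0.50 × 12 = 6 patients.
- Surgery uniform over days 14 to 28: the average of (28 − S)/28 over that range is (14 × 14/2)/(14 × 28) = 98/392 = 25%, or 3 patients.
- All surgery on day 28: 0.

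The result depends heavily on how late draws are actually taken. If draws are uniform over days 0 to 21 only, the share is (21 − 14)/21 = 33% (4 patients) with all surgery on day 14, and 7²/(2 × 14 × 21) = 49/588 = 8% (1 patient) with surgery uniform over days 14 to 28. If every draw is taken by day 14 and no surgery is earlier, the share is 0.

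**Step 3: cost of dropping post-operative samples.** With an unchanged SD, the standard error of the mean paired change grows by √(12/n) relative to 12 pairs:

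- 11 pairs: √(12/11) = 1.04, up 4%
- 9 pairs: √(12/9) = 1.15, up 15%
- 6 pairs: √(12/6) = 1.41, up 41%

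**Step 4: bias if the samples are kept.** The documents give neither the size nor the direction of any surgical effect on these markers, so this is not quantified.

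**The case against.** The strongest reply is that the intent is already plain. The analysis section labels the sample as pre-surgery, and it belongs to the same combined document as the schedule. Radiation Planning starts the window immediately after the last fraction. The assessment table puts the draw column before the prostatectomy column. OUTCOME MEASURES ties the first sample to completion of SBRT and the later ones to completion of treatment, which in that section includes surgery. Although the draw appears under Follow-up, after the Prostatectomy section, its bullet is timed from the final fraction; only the next bullet starts the post-surgery schedule. On its wording, the contrast arguably excludes a post-operative sample already, and staff who book the draw around surgery would leave few or none affected.

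Most of this stands. A reader might infer that the plan gives contradictory instructions or schedules the draw after surgery. It does neither: it omits an operational limit. A reader might also take 25% or 50% as expected losses. The documents do not support that, because every non-zero share rests on assumed uniform, independent timing, and the 50% also needs every operation on day 14.

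What the reply does not remove is the written window. A label in the analysis section is not a collection rule, and column order fixes no sequence when both columns span the same four weeks. It is also fair to say that a late sample need not be wasted: it can be left out of the contrast and still be described in the time course.

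**Conclusion.** The point holds as a missing collection rule that is worth correcting. The permitted window admits post-operative samples to a contrast meant to be pre-operative, and the plan states no handling for them. That the windows overlap is certain. The consequence is not: the number affected lies between zero and an unknown figure, with 3 or 6 of 12 only as illustrations under the assumptions shown. Any loss of precision follows from that number, and any bias cannot be sized from the documents.

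The effect is confined to a secondary correlative analysis. A reader might infer that the feasibility result is weakened; it is not, because treatment completion depends on the radiation given and the date of surgery, not on this blood sample.

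**What to change.** - In Secondary Objectives, Radiation Planning, Follow-up and the TABLE OF STUDY ASSESSMENTS, state that this research blood draw is taken after the final fraction and before prostatectomy.
- Record the draw date relative to the last fraction and relative to surgery.
- In the serological-markers paragraph of STATISTICAL CONSIDERATIONS, state that any post-operative draw is excluded from the pre-surgery contrast and that the number excluded is reported. Such a sample may still be described in the time course.

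The change concerns the blood draw only; it leaves surgery timing and the other assessments as they are. It costs a line in each place and two recorded intervals. There are two practical downsides. A draw will occasionally be missed when surgery comes first. And because Follow-up puts the draw at the same visit as the adverse event, EPIC and IPSS assessments, a separate draw is needed when that visit falls after surgery, unless blood is taken at the final-fraction visit, which the current window already allows.

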**OUTCOME MEASURES**

**Primary objective, feasibility:** A patient is considered to have completed treatment if they received the prescribed radiation dose of 24 Gy delivered in 3 fractions of 8 Gy within a span of 2 weeks and subsequently undergo prostatectomy within 4 weeks of completing radiotherapy.

**Secondary objective, safety and acute toxicity:** Patients will be evaluated during RT, prostatectomy, and at intervals of 3 months following completion of treatment for one year. At each visit, patients will complete the EPIC and IPSS questionnaires and will be assessed for CTCAE v4 toxicities.

**Secondary objective, correlative studies:** Assessments of the systemic immune response will utilize blood that is collected pretreatment, after completion of SBRT, and at 3 and 6 months post treatment completion. The local immune response (intratumoral) will utilize the resected prostatectomy specimen, pre-treatment biopsies, and archived tissue arrays of prostatectomy specimens that did not undergo RT. RNA- and exome-sequencing of irradiated prostate tumors will utilize the resected prostatectomy specimens, which will be compared to existing sequencing analyses of localized prostate cancers (TCGA) matched for histology and Gleason grade.

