### **Scientific impact**

RT causes genotoxicity in irradiated tissue, which is a primary cause of cancer cell killing (21). More recent evidence suggests that additional radiation-induced pathways are at play which drive immune recognition and tumor-immune eradication with potentially systemic consequences, especially after high dose per fraction RT (6–8). The promising synergy between RT and the immune system is underscored by a multitude of ongoing clinical trials that combine local irradiation with systemic immunomodulatory therapeutics. Translational studies correlating such systemic and intratumoral responses using freshly irradiated tissue, however, are extremely rare. Laboratory studies suggests that the doses used in prostate SBRT are close to the optimal fraction sizes to generate such measurable immunological changes. Therefore, this pre-operative prostate SBRT trial offers a unique opportunity to study the radiobiology of SBRT in the clinic, one that simply cannot be ignored.

Another level of complexity arises from the fact that RT may induce markers of EMT and neuroendocrine differentiation in prostate and other cancers, potentially promoting treatment resistance (22,23). If prostate radiotherapy drives such de novo transformations above what exists anyway, then strategies targeting these pathways would be particularly effective when combined with radiation. What's more, the hypothesis is that EMT transformations are promoted by pro-inflammatory conditions, which would suggest an alternative, and less favorable outcome for high-risk patients after receiving SBRT. Resolving the relative importance of EMT viz-a-viz immune system activation in individual patients is a novel and important long-term goal of this study. It will generate insight by studying both EMT and pro-inflammatory and immune SBRT-induced changes within the radiation-damaged microenvironment in vivo using IHC and transcriptomics. Currently, these changes are largely unknown. Therefore, we believe the correlative genomic analyses we have proposed would, at minimum, be hypothesis generating for future investigations with high translational impact.

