### **Study design:**

This is a single arm, Phase I feasibility study of SBRT followed by prostatectomy within 4 weeks for patients with prostate cancer at high risk of local failure after prostatectomy. A patient is considered to have completed treatment if they received the prescribed radiation and undergo prostatectomy within 4 weeks of completing radiotherapy.

NUMBER OF PATIENTS;

12 patients in 3 years with recruitment at UCLA Jonsson Comprehensive Cancer Center

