For comparison between post SBRT prostatectomy specimens and biopsy material pre-SBRT, average IntMax will be compared using a paired t-test or Wilcoxon signed-rank test (if the IntMax scores do not follow a normal distribution). For comparison between post SBRT prostatectomy specimens and archived material, average IntMax will be compared using a t-test or Wilcoxon rank-sum test (if the IntMax scores do not follow a normal distribution).

**RNA and DNA exome sequencing (secondary objective).** Quality control will be performed on the raw sequence data from RNA-seq experiments, which contain multiple short-read sequences with Phred quality score information using FastQC and FASTX-Toolkit. Bowtie2 will be used to align reads, which will then be mapped to the reference genome by TopHat2. Raw reads from exome sequencing will be aligned via BWA and converted to BAM format, and processed with the Genome Analysis Toolkit software package. Comparisons will be made to existing sequencing data (TCGA) for localized prostate tumors matched for histology and Gleason grade. Functional annotation will be performed using Gene Ontology, KEGG, and Reactome.

**Stopping Rules for Toxicity.** Prior studies evaluating RT prior to prostatectomy demonstrate safety of pre-operative RT at doses of up to 54 Gy in 30 fractions (12). It is anticipated that toxicity in this study will be low because our dose is selected based on the prior studies.

Nevertheless, our trial will be stopped for toxicity if any treatment related toxicity of CTCAE v4.0 grade 3 or above is observed in more than two subjects during the study

period in the following categories: gastrointestinal, urinary, with the exception of temporary use of a catheter and urinary incontinence, which can occur after prostatectomy in the absence of radiotherapy.

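### Irradiated trial specimens are sequenced against TCGA data alone, so the comparison can show differences from TCGA but not which pathways irradiation enriched

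*Combined protocol and SAP*

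**What the plan says.** All references are to the combined protocol and SAP.

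- **Aim.** The Secondary Objectives state the purpose of the RNA-seq work as "Pathway activation from RNA-seq data sets in order to determine which pathways are enriched after irradiation". Scientific impact puts the question causally, "If prostate radiotherapy drives such de novo transformations above what exists anyway", and describes the genomic work as hypothesis generating at the least.
- **Samples sequenced.** The Secondary Objectives say that "prostate lesions at the time of prostatectomy will be processed for RNA and exome sequencing". No section plans sequencing of pre-SBRT biopsies, of non-irradiated local specimens, or of any bridging sample.
- **Comparator.** Outcome Measures says: "RNA- and exome-sequencing of irradiated prostate tumors will utilize the resected prostatectomy specimens, which will be compared to existing sequencing analyses of localized prostate cancers", and names these as TCGA. The sequencing paragraph of Statistical Considerations agrees: "Comparisons will be made to existing sequencing data (TCGA) for localized prostate tumors matched for histology and Gleason grade".
- **Design and size.** Study design says "This is a single arm, Phase I feasibility study of SBRT followed by prostatectomy within 4 weeks", with "12 patients in 3 years with recruitment at UCLA Jonsson Comprehensive Cancer Center".
- **Processing.** The sequencing paragraph lists FastQC and FASTX-Toolkit for quality control, Bowtie2 and TopHat2 for RNA reads, and BWA and the Genome Analysis Toolkit for exome reads. It describes no batch handling and does not say whether the TCGA reads go through the same steps.
- **Other non-irradiated tissue.** Pre-SBRT biopsies and archived non-irradiated prostatectomy specimens are compared with trial specimens, but only for the immunohistochemistry (IHC) markers.

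**The concern.** The aim attributes pathway changes to irradiation. In the data to be analysed, having been irradiated and having been sequenced by this trial are the same property. Any systematic difference between the trial's samples and the TCGA dataset would appear as a pathway difference and could be read as a radiation effect.

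Matching on histology and Gleason grade deals with part of the case mix. It does nothing about how tissue was handled, how libraries were prepared, when and where samples were sequenced, or which software processed the reads. ADT is a further difference: the Eligibility Criteria permit it, and it is not a matching variable.

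At stake is the interpretation of one secondary analysis and the hypotheses carried from it into later work.

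**Working it through.** The documents give no sample size, alpha, power or decision rule for the sequencing comparison, so there is no planned figure to reproduce. The check is whether the irradiation effect can be identified.

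**Inputs from the documents.** At most 12 irradiated trial tumors; no concurrent control arm; TCGA as the only named comparator.

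**Assumptions.** The TCGA tumors were not irradiated, as the planned contrast requires. The number of matched TCGA tumors is m = 12 to 300. A dataset shift, where present, is s = 0.25 to 1.5 SD. The documents state none of these.

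**Step 1: identifiability.** For one gene, write

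Y = a + b·R + d·D + error,

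where R = 1 if irradiated and D = 1 if sequenced by the trial. For every trial sample R = D = 1, and for every TCGA sample R = D = 0. The model reduces to

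Y = a + (b + d)·R + error.

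The difference in means estimates b + d, and nothing in the data splits the sum. The matrix [intercept, R, D] has rank 2 with 3 columns for m = 12, 50, 100 and 300, and the correlation of R with D is 1.0. A batch-correction term is the D column, so it would remove b together with d. Neither more patients nor more TCGA tumors change this. The result needs no assumption about s.

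**Step 2: possible consequence.** Take genes with no irradiation effect (b = 0) and a dataset shift of s. The table shows the share of 20,000 simulated genes rejected by a two-sided t-test at 0.05, with 12 trial samples against m TCGA samples.

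| Assumed shift s (SD) | m = 12 | m = 50 | m = 100 | m = 300 |
|---|---|---|---|---|
| 0 | 5.0% | 5.2% | 5.2% | 5.1% |
| 0.25 | 8.9% | 11.9% | 12.4% | 13.2% |
| 0.5 | 21.8% | 33.5% | 37.4% | 39.0% |
| 1.0 | 65.4% | 86.4% | 89.8% | 92.3% |
| 1.5 | 94.1% | 99.6% | 99.8% | 99.9% |

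Hand check for s = 0.5 and m = 100: the noncentrality is 0.5 / √(1/12 + 1/100) = 0.5 / 0.3055 = 1.64. The critical value on 110 degrees of freedom is about 1.98. The rejection probability is about Φ(1.64 − 1.98) = Φ(−0.34) ≈ 0.37, in line with the table. For a given shift, a larger comparator makes matters worse, because the test becomes more precise about b + d.

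**Step 3: what would break the overlap.** Non-irradiated samples handled and sequenced together with the trial samples have R = 0 and D = 1, and they raise the rank to 3 of 3. With 12 such samples against 12 irradiated ones, the simulated rejection rate stays at about 5% for every assumed shift. The plan contains no such samples for sequencing.

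**The case against.** **The analysis is secondary and exploratory.** It has no test or decision rule, and the primary endpoint is treatment completion. That stands and limits the weight of the point. It does not rescue the stated aim, which attributes enrichment to irradiation. A hypothesis drawn from a dataset difference may be a processing artefact.

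**Joint processing may already be intended.** Statistical Considerations speaks of existing TCGA data in the same paragraph as the raw-read pipeline, whereas Outcome Measures speaks of existing analyses. A reader might infer that already processed TCGA results will be used. The documents do not settle this, so it should be stated. The sequencing laboratory is also not named; that TCGA was produced elsewhere is inferred from its being existing data.

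**The IHC comparisons supply internal controls.** They bear on the EMT and neuroendocrine questions, which Scientific impact assigns to IHC as well as transcriptomics. A reader might go further and treat a pathway as radiation-induced when it moves in the same direction as a paired IHC marker. The documents do not support that rule:

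- In the paired contrast, every pre-SBRT sample is a biopsy and every post-SBRT sample is a prostatectomy specimen.
- If neither contrast has a true effect and their signs are independent, they agree with probability 0.5 × 0.5 + 0.5 × 0.5 = 0.5.
- ADT begun between biopsy and surgery could move the same markers in both contrasts.
- Pre-treatment tissue is compared only where possible, so fewer than 12 pairs may exist.

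**Conclusion.** The point holds for the RNA and exome sequencing comparison. Irradiation and data source coincide completely, so the data can describe how post-SBRT specimens differ from TCGA tumors but cannot attribute those differences to irradiation. This follows from the design, given that the TCGA tumors were not irradiated.

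The size of any bias is unknown. The false-positive rates above illustrate assumed shifts and comparator counts and do not forecast this trial. A reader might infer that the pathway findings will be mostly artefact or that the sequencing has no value. The documents do not support that either: real radiation effects may be present, and the data can still suggest hypotheses if they are labelled for what they are.

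The primary feasibility endpoint, the safety assessment and the IHC comparisons are not affected.

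**What to change.** 1. **Statistical Considerations, sequencing paragraph.** State that raw reads of the matched TCGA tumors will, where accessible, go through the same quality control, Bowtie2/TopHat2 and BWA/GATK steps as the trial samples. Say that this removes only the pipeline part of the confounding; tissue handling, library preparation and sequencing batch remain.
2. **Secondary Objectives and Outcome Measures.** Restate the sequencing aim and its conclusions as pathways that differ between post-SBRT specimens and TCGA tumors, not attributable to irradiation from these data alone. Report the trial patients' ADT status with the results.
3. **Use of IHC.** Cite IHC findings only as supporting context. Do not use directional agreement with them to label a pathway radiation-induced.

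The cost is some computing work, wording changes and a more modest claim. No new samples or patient procedures are needed. The documents do not say whether the TCGA raw reads are accessible to the team; if they are not, the second and third changes still apply.
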